1.4 Rationale for Study Design

This study will evaluate the immunologic and cytotoxic changes induced by ibrutinib in prostate tissues compared to pretreatment biopsies. Three patients were enrolled at the 840 mg/d x 2 weeks dose level at UCSF and no DLTs were seen. A safety lead-in consisting of 6 patients will be enrolled at the 840 mg/d x 4 weeks dose level to evaluate the safety and tolerability of ibrutinib administered for 4 weeks preoperatively in patients scheduled for RP. If fewer than 2 DLTs are seen, an additional 18 patients will be treated with ibrutinib at the 840 mg/d x 4 weeks dose level before undergoing RP.

The safety profile of ibrutinib is well established from multiple studies in subjects treated with single agent ibrutinib (1061 subjects with B cell malignancies, 143 healthy subjects). Ibrutinib is generally well tolerated, and treatment related adverse events are generally manageable. The rationale for studying ibrutinib at dose of 840mg is that the dose of ibrutinib required for activity in solid malignancies via immune modulation and/or direct cytotoxicity may be higher than 560mg, the dose currently approved for hematologic malignancies. In the phase 1 study of ibrutinib in relapsed or refractory B-cell NHL and B-cell CLL, MTD was not reached after dose escalation from 2.5mg/kg/day to 12.5mg/kg/day (Advani RH et al. J Clin Oncol 2012). The phase 1b/2 study of ibrutinib in relapsed/refractory CLL or small lymphocytic lymphoma showed similar efficacy and toxicity profiles of ibrutinib administered at 420mg and 840mg (Byrd JC, et al. N Engl J Med 2013). Recently, interim data from an open label phase 2 study of ibrutinib combined with dexamethasone in relapsed/refractory multiple myeloma showed manageable toxicities at a dose up to 840mg (Vij R et al. ASH 2014). We therefore believe that the dose of ibrutinib 840mg will be well tolerated in patients with localized prostate cancer.

1.5 Correlative Studies

This study aims to evaluate the immunomodulatory and cytotoxic effects of ibrutinib in prostate cancer patients by comparing their pre-treatment prostate biopsy tissue to post-treatment prostatectomy tissue. Specifically, immunohistochemistry and genomic analysis will be carried out to analyze the following:

1. Characterize the tumor and immune cell subsets
2. Explore the location of tumor infiltration lymphocytes (e.g., tumor center, tumor and benign tissue interface)
3. Characterize BCR and TCR clonality and diversity
4. Examine PD-L1 expression in tumor and immune-infiltrating immune cells
5. Examine Btk expression in B cells and tumor cells
6. Assess rate of downstaging and pT0 rate
7. Assess rate of PSA decline

In addition, serum and blood will be analyzed to characterize circulating immune cell subsets in response to treatment.

2 OBJECTIVES AND ENDPOINTS OF THE STUDY

2.1 Objectives

2.1.1 Primary Objectives

1. To assess safety in patients with localized prostate cancer.
2. To characterize B and T cell infiltration within prostate tissue of men with localized prostate cancer treated with neoadjuvant ibrutinib, and to compare B and T cell infiltration to a reference population of untreated patients who underwent RP.

2.1.2 Secondary Objectives

1. To characterize changes in the frequency and number of circulating B and T cells induced by neoadjuvant ibrutinib in patients with localized prostate cancer.
2. To determine the cytotoxic effect and clinical benefit of neoadjuvant ibrutinib in men with localized prostate cancer.

2.1.3 Exploratory Objectives

1. To examine Btk expression in prostate tumor cells and tumor-infiltrating B cells at baseline before neoadjuvant ibrutinib treatment and at RP after treatment.
2. To determine the impact of neoadjuvant ibrutinib on PD-L1 expression in prostate cancer cells and tumor-infiltrating lymphocytes (TILs).
3. To determine the effects of neoadjuvant ibrutinib on T and B cell repertoire within the tumor and blood.

2.2 Endpoints of the Study

2.2.1 Primary Endpoints

The primary endpoint of the safety-run in part is adverse events (AEs), especially dose limiting toxicity (DLT), as defined in Section 6.1.4.

The primary endpoint of the phase II study include: the change in infiltration of CD20+ B cells, IL-10+ B cells, CD3+ T cells, CD8+ cytotoxic T cells, effector CD4+FOXP3- T cells, and CD4+FOX3+ T regulatory cells in pre-treatment biopsy, RP tissue, and reference RP tissue quantitated by immunohistochemistry (IHC). Patients will be considered to have a positive response if there is ≥ 2 fold decrease from pre-treatment to post-treatment, or considered to have a negative response if there is < 2 fold decrease. The proportion of patients who have “positive” responses will be evaluated.

2.2.2 Secondary Endpoints

The changes in the frequency and number of circulating CD19+ B cells, CD25^{high}CD27^{high}CD86^{high} B regulatory cells, and CD3+, CD8+, CD4+FOXP3- and CD4+FOXP3+ T cells induced by neoadjuvant ibrutinib in patients with localized prostate cancer by flow cytometry. Patients will be considered to have a positive response if there is ≥ 2 fold decrease from pre-treatment to post-treatment, or considered to have a negative response if there is < 2 fold decrease. The proportion of patients who have “positive” responses will be evaluated.

The proportion of patients who achieve $\geq 50\%$ PSA decline, pathologic down-staging and/or pathologic T0 at RP after neoadjuvant ibrutinib in men with localized prostate cancer.

2.2.3 Exploratory Endpoints

To examine Btk expression in prostate tumor cells and tumor-infiltrating B cells in pre-treatment and post-RP tissue via immunohistochemistry with anti-Btk antibody.

To examine the change in PD-L1 expression in prostate cancer cells and tumor-infiltrating lymphocytes induced by neoadjuvant ibrutinib via immunohistochemistry with anti-PD-L1 antibody.

To determine the change in T and B cell repertoire within the tumor and blood with neoadjuvant ibrutinib via deep sequencing of VDJ regions of TCRs and BCRs.

3 STUDY DESIGN

3.1 Characteristics

This is a single center phase 2 open label study starting with a safety lead-in ibrutinib administered as neoadjuvant therapy in patients with localized prostate cancer. We believe that the dose of ibrutinib 840mg x 4 weeks will be well tolerated in patients with localized prostate cancer based on current trial data on ibrutinib but to ensure safety, we will start with a safety run-in. Previously at UCSF, 3 patients were enrolled to the 840 mg/d x 2 weeks dose level. No DLTs were observed. Beginning at WUSM, patients will be enrolled at the dose level of 840 mg/d x 4 weeks. If there are fewer than 2 DLTs, the Phase II dose expansion study will open and enroll up to an additional 18 patients to be treated with ibrutinib 840mg PO daily for 4 weeks.

If there are ≥ 2 DLTs in the safety lead-in, dosing will be de-escalated as follows:

- Level -1: 840 mg/d x 2 weeks, followed by de-escalation if ≥ 2 DLTs to Level -2
- Level -2: 560 mg/d x 2 weeks

In each enrolled patient, neoadjuvant ibrutinib therapy will be followed by radical prostatectomy (RP) performed 7 to 12 days after the last dose of ibrutinib. Pre-treatment and RP tissue will be evaluated for immunologic characterization, Btk expression and pathologic response. The proportion of patients achieving $\geq 50\%$ PSA decline will be assessed. Serum will also be obtained to characterize circulating immune response. All patients will be followed clinically for 4 weeks after RP to monitor for adverse events.

3.2 Number of Subjects

The safety lead-in part requires 6 patients at the 840 mg/d x 4 weeks dose level. The phase II study will require a total of 24 patients (6 in the safety lead-in plus an additional 18). A sequential stopping rule is in place during Phase II (see Section 12.5).

If RP is delayed to over 12 days after the last dose of ibrutinib therapy (i.e. from scheduling delay of RP), a replacement patient will be accrued. The maximum number of allowed replacement patients is 4 (see Section 12.4).

To date, 3 patients have been enrolled and treated at UCSF (PI: [name]) in Phase I/Cohort I (840 mg x 2 weeks) with no DLTs noted to date.

3.3 Eligibility Criteria

Patients must have baseline evaluations performed prior to the first dose of study drug and must meet all inclusion and exclusion criteria. In addition, the patient must be thoroughly informed about all aspects of the study, including the study visit schedule and required evaluations and all regulatory requirements for informed consent. The written informed consent must be obtained from the patient prior to enrollment. The following criteria apply to all patients enrolled onto the study unless otherwise specified.

3.3.1 Inclusion Criteria

1. 18 years of age or older
2. ECOG performance status 0 or 1
3. Histologically documented adenocarcinoma of the prostate
4. Patients must be suitable for and willing to undergo a radical prostatectomy at the completion of study therapy.
5. Adequate bone marrow function, defined as:
 - o WBC >2,500 cells/mm³
 - o ANC >1,500 cells/mm³
 - o Hemoglobin >9 mg/dL
 - o Platelet count >100,000 cells/mm³
6. Adequate renal function, defined as serum creatinine <2 mg/dL or CrCl >30 mL/min
7. Adequate liver function, defined as:
 - o AST and ALT <2.5x institutional ULN
 - o Serum bilirubin <1.5x institutional ULN
8. Adequate coagulation function, defined as normal PT/INR and PTT
9. Ability to understand and willingness to sign a written informed consent document
10. Available evaluable archival tumor tissue for correlative studies including assessment of immune infiltration and Btk expression is required. If archival tissue is unavailable, patients must be willing to undergo repeat prostate biopsy. Tissue is considered sufficient for correlative endpoint analyses if they are obtained from at least 2 prostate cores and consist of at least 15 unstained slides from the largest tumor volume and/or highest Gleason score. The availability of archival tissue or consent for repeat prostate biopsy is required for study eligibility; determination of tissue sufficiency is not required for study

eligibility.

11. The effects of ibrutinib on the developing human fetus is unknown. Men treated or enrolled on this protocol must agree to use adequate contraception prior to the study, for the duration of the study participation, and for 3 months after completion of treatment.

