Unique Aspects of this Study	
This is the first study to evaluate the safety of ibrutinib and its effect on B cell infiltration in the neoadjuvant setting for patients with localized prostate cancer. The secondary and exploratory objectives will enhance our understanding of the immunomodulatory and cytotoxic effects of Btk inhibition in prostate cancer. Findings may justify further exploration of ibrutinib in prostate cancer, including combinational therapy in advanced prostate cancer.

List of Abbreviations

5-HT	5-hydroxytryptamine (serotonin)
ADL	activity of daily living
ADT	androgen deprivation therapy
AE	adverse event
ALP	alkaline phosphatase
ALT	alanine aminotransferase
ANC	absolute neutrophil count
AST	aspartate aminotransferase
ATC	Anatomical Therapeutic Chemical (Classification System)
AUC	area under the curve
B-CLL	B-cell chronic lymphocytic leukemia
BCR	B-cell receptor
Breg	B regulatory cells
BSA	body surface area
BTK	Bruton's tyrosine kinase
BUN	blood urea nitrogen
CAPRA	Cancer of the Prostate Risk Assessment
CBC	complete blood cell (count)
CHR	Committee on Human Research (UCSF IRB)
CpG	cytosine-phosphate-guanine
CNS	central nervous system
CR	complete response
CRC	Clinical Research Coordinator
CrCl	creatinine clearance
CRF	case report form
CSF	cerebral spinal fluid
CT	computerized tomography
CTCAE	Common Terminology Criteria for Adverse Events
CTEP	Cancer Therapy Evaluation Program
CTL	cytotoxic T lymphocyte
CTLA-4	cytotoxic T-lymphocyte-associated protein 4
CTMS	Clinical Trial Management System
CYP	cytochrome P450
DFS	disease-free survival
DL	dose level
DLBCL	diffuse large B-cell lymphoma
DLT	dose limiting toxicity
D2	dopamine receptor D2
DSMC	Data and Safety Monitoring Committee
DSMP	Data and Safety Monitoring Plan
EC ₅₀	median effective concentration
ECG	Electrocardiogram
ECOG	Eastern Cooperative Oncology Group
FCBP	female of childbearing potential
FDA	Food and Drug Administration
FIH	first-in-human
FL	follicular lymphoma
GCP	Good Clinical Practice
g/dL	gram per deciliter
Hb	Hemoglobin
HBcAb	Hepatitis B core antibody
HBeAg	Hepatitis B "e" antigen
HBsAb	Hepatitis B surface antibody
HBsAg	Hepatitis B surface antigen

List of Abbreviations

HBV	hepatitis B virus
HCT	Hematocrit
HCV	hepatitis C virus
HDFCCC	Helen Diller Family Comprehensive Cancer Center
HED	human equivalent dose
HGB	Hemoglobin
HIV	human immunodeficiency virus
IB	investigator's brochure
IC ₅₀	concentration that inhibits a process by 50%

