6.2 Dose Modifications for an Individual Patient Regardless of Dose Cohort

If a patient experiences any CTCAE v4.0 grade 4 toxicity attributed to treatment, ibrutinib must be discontinued. If a patient experiences any CTCAE v4.0 grade 3 toxicity attributed to treatment, ibrutinib must be held until resolution of the toxicity to grade 1 or the patient's baseline, at which time the patient may resume ibrutinib at 50% of the starting dose. If the patient experiences recurrence of the same grade 3 toxicity while on 50% reduced dose,

ibrutinib must be discontinued. If a grade 3 toxicity does not resolve to grade 1 or the patient's baseline within 2 weeks of holding therapy, ibrutinib must be discontinued.

Ibrutinib Dose Modifications According to Toxicity

Event	Management
Any grade 4 toxicity attributed to treatment	Discontinue ibrutinib
Any grade 3 toxicity attributed to treatment	Hold ibrutinib until \leq grade 1, then resume ibrutinib at 50% starting dose
Recurrence of the same grade 3 toxicity while on half dose	Discontinue ibrutinib
Grade 3 toxicity not resolving to \leq grade 1 within 2 weeks	Discontinue ibrutinib

Clinical judgment of the treating physician should guide the management plan of each patient based on individual benefit/risk assessments.

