Grade 2 (10-30% BSA covered with or without symptoms; limiting instrumental ADL)	Review medications for other potential drug etiologies and discontinue suspected agent(s) as appropriate. Use topical or oral antihistamines for symptomatic relief. Topical corticosteroids may be used if clinically indicated. Avoid systemic corticosteroids which has systemic immunomodulatory effects and may affect study endpoints. If symptoms are prolonged (e.g., >2 weeks) and do not improve, reduce the starting dose of ibrutinib by 140mg.

Toxicity and Intensity	Dose Modification and Suggestions for Management
Grade 3 (>30% BSA covered with or without symptoms; limiting self care ADL)	Review medications for other potential drug etiologies and discontinue suspected agent(s) as appropriate. Use topical or oral antihistamines for symptomatic relief. Topical corticosteroids may be used if clinically indicated. Avoid systemic corticosteroids which has systemic immunomodulatory effects and may affect study endpoints. Hold ibrutinib until rash \leq grade 1, and then resume at 50% of the starting dose.
Anemia (very common)	
Grade 1 (Hb <LLN-10.0 g/dL)	Maintain ibrutinib dose level. Assess for evidence of gastrointestinal bleeding.
Grade 2 (Hb <10.0-8.0 g/dL)	Assess for evidence of gastrointestinal bleeding. Hold ibrutinib until anemia is resolved to \leq grade 1, at which time resume ibrutinib at 140mg lower than the starting dose.
Grade 3 (Hb <8.0 g/dL, transfusion indicated)	Transfuse PRBC per standard institutional practices. Hold ibrutinib until anemia \leq grade 1, and then resume at 50% of the starting dose. Red blood cell growth factors (erythropoietin) are permitted per institutional policy and in accordance with the ASCO guidelines. Short doses of steroids for autoimmune cytopenias are permitted for <14 days at doses that do not exceed 100 mg per day of prednisone or equivalent.
Thrombocytopenia (very common)	
Grade 1 (Plt <LLN- 75,000/mm ³)	Check manual blood smear to rule out pseudothrombocytopenia. Maintain ibrutinib dose level.
Grade 2 (Plt <75,000-50,000/mm ³)	Check manual blood smear to rule out pseudothrombocytopenia. Hold ibrutinib until thrombocytopenia is resolved to \leq grade 1, at which time resume at 140mg lower than the starting dose.

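### The haemoglobin entry limit is printed in mg/dL instead of g/dL, so taken literally it excludes nobody (minor, one-unit correction)

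*Combined protocol and SAP*

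**What the plan says.** Section 3.3.1, item 5, defines adequate bone marrow function by four laboratory limits. White cells, neutrophils and platelets are each given per mm³. The haemoglobin limit is "Hemoglobin >9 mg/dL".

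The opening of Section 3.3 makes the criteria binding: patients "must meet all inclusion and exclusion criteria". Section 4.1 requires a completed, signed eligibility checklist with source documents before registration.

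Elsewhere the protocol measures haemoglobin in g/dL. The List of Abbreviations defines g/dL as "gram per deciliter". The toxicity table in Section 6.3 gives its anaemia rows in that unit, including "Grade 2 (Hb <10.0-8.0 g/dL") and "Grade 3 (Hb <8.0 g/dL, transfusion indicated").

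No other section restates or corrects the entry limit, and no other criterion sets a numeric haemoglobin floor. Exclusion 26 does not fill the gap. It concerns unresolved toxicity from earlier anti-cancer therapy, and its alternative test refers back to the levels in the eligibility criteria.

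**The concern.** An eligibility limit is an operative instruction: a coordinator compares a laboratory value with it and records a pass or a fail. A limit of 9 mg/dL cannot produce a fail, so the haemoglobin line of item 5 does no screening if it is followed as printed. If the line was copied unchanged into the eligibility checklist, the checklist has the same defect. The checklist is not among the documents, so this cannot be confirmed.

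The setting gives a working floor some clinical purpose. Every patient takes a drug for which Section 1.2.2.1 reports major haemorrhage, and then has a radical prostatectomy. What is at stake is whether the written protocol states the limit that was meant, and whether eligibility can be verified against it.

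**Working it through.** **Inputs**

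- Entry limit as printed: 9 mg/dL (Section 3.3.1, item 5).
- Boundary between grade 1 and grade 2 anaemia: 10.0 g/dL (Section 6.3, anaemia rows).
- Boundary between grade 2 and grade 3 anaemia: 8.0 g/dL (same rows).
- Conversion: 1 g = 1,000 mg.

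**Step 1. Convert the printed limit.** 9 mg/dL ÷ 1,000 = 0.009 g/dL.

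**Step 2. Compare it with the protocol's own anaemia grades.**

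| Section 6.3 boundary | In mg/dL | Ratio to the printed limit |
|---|---|---|
| 10.0 g/dL (grade 1/2) | 10.0 × 1,000 = 10,000 | 10,000 ÷ 9 = 1,111 |
| 8.0 g/dL (grade 2/3) | 8.0 × 1,000 = 8,000 | 8,000 ÷ 9 = 889 |

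A man just below 8.0 g/dL has just under 8,000 mg/dL. Section 6.3 would grade that as 3, with transfusion indicated, yet he clears a limit of 9 mg/dL by a factor of nearly 889. The literal criterion passes him.

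**Step 3. Apply the corrected unit.** 9 g/dL × 1,000 = 9,000 mg/dL, which is 1,000 times the printed limit. The same man now fails, since 8,000 is below 9,000. Read this way, the limit falls between the two Section 6.3 boundaries (8.0 < 9 < 10.0) and works as an ordinary entry floor.

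**Step 4. Check whether the unit might be deliberate, or damaged in the text.** Three comparisons argue against both.

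- Neutrophils and platelets appear in item 5 and again in Section 6.3, per mm³ in both places. Of the marrow limits that recur, only haemoglobin changes unit.
- The printed unit is a clean, complete string, with no sign of a broken table or a redaction.
- mg/dL is the right unit for creatinine in the next item of the same list. It may have carried over from there, but the documents do not say.

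No sample-size or power calculation applies, because no alpha, power, patient number or response rate depends on this limit.

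**The case against.** The strongest reply is that this is a misprint with no shown consequence. Nobody chose mg/dL. A haemoglobin limit of 9 has only one sensible reading, and site staff would almost certainly supply it. The factor of 1,000 describes the size of a slip in a unit and does not measure harm. Other safeguards also remain. Inclusion 4 requires suitability for radical prostatectomy. Exclusion 15 covers conditions that would make ibrutinib hazardous or obscure adverse events. Exclusion 25 lets the investigator exclude a man whose condition could compromise his safety.

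Most of this stands, and it sets the severity. It does not remove the point, for two reasons. The remaining safeguards rest on judgement, whereas item 5 is the only numeric haemoglobin limit. And the misprint sits in a binding threshold, not in background text.

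A reader might infer that severely anaemic men will be enrolled, or that the safety data or the primary analysis are compromised. The documents do not support that. They show only what the criterion says when taken literally. They give no evidence that anyone would apply it that way, and the judgement-based criteria still operate.

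A reader might also note that >9 g/dL admits men above 9.0 and below 10.0 g/dL, within the Section 6.3 grade 2 range, and infer that the corrected limit is itself wrong. That does not follow either. The Section 6.3 table manages toxicity related to ibrutinib, and Section 7 sends baseline events to the medical history form. Entering in that range therefore does not in itself trigger a hold. Where to set the floor is a clinical choice for the sponsor.

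**Conclusion.** The criterion is wrong as written, and the severity is minor. The printed limit is 0.009 g/dL where 9 g/dL is evidently meant, an error by a factor of 1,000, and taken literally it excludes nobody. That statement applies to this one line, not to the eligibility criteria as a whole.

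The conclusion rests on one reading: that g/dL was intended. The anaemia rows in Section 6.3 and the abbreviation list support this, and nothing in the documents points the other way. The expectation that sites would read the limit correctly is an assumption. It is a very likely one, but the documents do not test it.

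No effect on enrolment, sample size, power, endpoints or the analysis is claimed.

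**What to change.** In Section 3.3.1, item 5, change the haemoglobin line to: Hemoglobin >9 g/dL. Check that the eligibility checklist required by Section 4.1 carries the same value and unit, and correct it if it does not.

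The cost is one unit in the next amendment and one look at the checklist. The change needs no new test, since the complete blood count is already a screening assessment. It leaves the intended population as it is and has no statistical consequence.

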8.1.1.2 Screening Assessments

The Screening procedures and assessments must be completed within 28 days of the first day of ibrutinib.

- Physical examination
- Vital signs
- Complete medical history
- Documentation of disease assessment
- ECOG Performance status
- Baseline concomitant medications taken within 28 days of Day 1
- Complete blood count (CBC) with differential and platelet count
- Blood chemistry assessment, including alkaline phosphatase, aspartate aminotransferase (AST), alanine aminotransferase (ALT), total bilirubin, calcium, phosphorus, blood urea nitrogen (BUN), creatinine, total protein, albumin, glucose, potassium, sodium, chloride, bicarbonate, lactate dehydrogenase (LDH)
- Coagulation assessment, including prothrombin time, partial thromboplastin time, international normalized ratio (PT/PTT/INR)
- PSA
- Hepatitis B surface antigen, anti-HBc antibody and anti-HBs antibody. In patients who have positive serology for the anti-HBc antibody, HBV DNA should be collected prior to Cycle 1, Day 1.
- HCV serology (anti-HCV antibody)
- HIV screening in accordance with national and/or institutional guidelines
- Serum collection in eight 10mL EDTA tubes for immune analyses to be sent to the TPC at Washington University
- Electrocardiogram (ECG)
- Pre-treatment tissue for correlative studies. If adequate tissue is available from a prior biopsy or surgery, samples will be requested from the hospital or clinic pathology department. If adequate tissue from a prior biopsy is not available, a prostate biopsy is required to participate in the study. There must be a minimum of 3 days between prostate biopsy and start of study drug.

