12.3 Sample Size and Power Estimate

For this phase 2 study, the primary endpoint is the change of B cells between the pre-treatment biopsy and post-treatment RP specimen. Each patient's response to neoadjuvant ibrutinib will be a binary classification. Patients will be considered to have a

“positive” response if there is >2 fold decrease in the number of B cells, or considered to have a “negative” response if there is <2 fold decrease in the number of B cells. The accrual of 18 patients to the phase 2 trial and incorporation of 6 patients who received ibrutinib at MTD in the safety lead-in (a total of 24 evaluable subjects) will be sufficient to determine whether 20% or more of the cohort achieves this 2 fold decrease in B cells, compared to a null response of 5% or less of a reference group of patients who underwent RP without neoadjuvant treatment. This comparison has a power of 0.818 at a significance level of 0.044 based on a one-sided binomial exact test. If 4 more evaluable patients show a “positive” response, the treatment achieves the expected “response” rate of 20%.

The safety-run in will require 6 patients (with a potential for 6-12 more if dose de-escalation is required). The Phase II study will require a total of 24 patients on MTD and thus 18 additionally enrolled patients besides the 6 on MTD during the safety lead-in.

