12.4 Replacement Policy

All patients who receive a dose of ibrutinib will be analyzed for safety and efficacy. Subjects who discontinue from study participation prior to receiving any dose of study therapy may be replaced. Subjects who have received any dose of study therapy will not be replaced for the safety and efficacy endpoints. Patients removed from study for unacceptable treatment related adverse event(s) will be followed until resolution or stabilization of all treatment related AEs to grade 2 or lower. However, they will not be replaced. Patients enrolled during the safety lead-in who discontinue treatment during the DLT observation period for reasons other than a DLT will need to be replaced for DLT purposes.

Because there is a potential for loss of immune cell infiltration within the prostate tissue after >12 days of not receiving ibrutinib, any patient who undergoes RP after 12 days from the last dose of ibrutinib (i.e. from scheduling delay of RP) will be included in the final analysis; however, an additional patient will be accrued as replacement. This will keep the treatment uniform in order to evaluate for immune response. The maximum number of allowed replacement patients for delayed RP is 4.

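### Power in Section 12.3 is 0.736, not 0.818, for 24 evaluable men under the exact test it names, and the plan does not secure 24 evaluable men

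*Combined protocol and SAP*

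**What the plan says.** **Power.** Section 12.3 bases the phase 2 comparison on "a total of 24 evaluable subjects", made up of 6 lead-in men and 18 more. The alternative of interest is that "20% or more of the cohort achieves this 2 fold decrease in B cells". The null rate is at most 5%, attributed to untreated men who had prostatectomy. The section then states: "This comparison has a power of 0.818 at a significance level of 0.044 based on a one-sided binomial exact test". The cutoff sentence is missing a word; I read it as four or more responders.

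**Enrolment.** Section 3.2: "The phase II study will require a total of 24 patients". This is the same number as the evaluable target.

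**Baseline tissue.** Inclusion criterion 10 in Section 3.3.1 asks for evaluable archival tissue, or willingness to have a repeat biopsy if none is available. It defines tissue as sufficient for the correlative analyses at two or more cores and 15 or more unstained slides. It then adds that "determination of tissue sufficiency is not required for study" eligibility. Section 8.1.1.2 reads differently: "If adequate tissue from a prior biopsy is not available, a prostate biopsy is required to participate in the study". It does not define adequate or refer to the criterion 10 standard.

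**Replacement.** Section 12.4: "Subjects who have received any dose of study therapy will not be replaced for the safety and efficacy endpoints". There are two exceptions: up to 4 extra men where prostatectomy falls more than 12 days after the last dose (the delayed men stay in the analysis), and lead-in men replaced for DLT assessment.

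**Analysis set.** Section 12.6.1 analyses every dosed man for efficacy. Neither it nor Section 12.6.2.2 says how a man without a usable pair is handled.

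**The concern.** Two separate things are at issue.

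First, the stated power and alpha should follow from the stated number, rates, cutoff and test. If they do not, the trial has been sized on a figure it does not have.

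Second, under Section 9.1.2 the endpoint is each man's post-treatment to pre-treatment ratio of cell density, so a man with no usable baseline has no endpoint. Read literally, criterion 10 lets such a man be enrolled and dosed. An untreated baseline cannot be obtained after Day 1, and no replacement rule covers him. With enrolment equal to the evaluable target, there is nothing to absorb the loss. Because his handling is not specified, the denominator of the reported proportion could be settled after the data are seen.

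**Working it through.** **Inputs (Section 12.3).** n = 24 evaluable, p0 = 0.05, p1 = 0.20, success if X ≥ 4, one-sided exact binomial. Stated result: alpha 0.044, power 0.818.

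**Step 1: reproduce the stated figure.** P(X ≥ 4) = 1 − [P(0) + P(1) + P(2) + P(3)], with P(k) = C(n,k) p^k (1−p)^(n−k).

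- n = 24, p = 0.05: 1 − (0.2920 + 0.3688 + 0.2232 + 0.0862) = **0.030** (alpha).
- n = 24, p = 0.20: 1 − (0.0047 + 0.0283 + 0.0815 + 0.1493) = **0.736** (power).

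The stated pair is not reproduced. Other cutoffs at 24 do not rescue it: three or more gives 0.116 and 0.886; five or more gives 0.006 and 0.540.

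**Step 2: what does fit.** Over n = 16 to 31 and cutoffs 3 to 5, only n = 27 with cutoff 4 matches both figures:

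- p = 0.05: 1 − (0.2503 + 0.3558 + 0.2434 + 0.1068) = 0.0437.
- p = 0.20: power 0.8177.

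A one-sided normal approximation at n = 24 with nominal alpha 0.044 also gives 0.818: (0.15 − 1.706 × 0.0445) / 0.0816 = 0.908, and Φ(0.908) = 0.818. That is not the exact test named, and the rule of 4 or more in 24 still has an actual alpha of 0.030.

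**Step 3: loss of pairs, cutoff kept at 4.** The number lost is an assumption.

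| Evaluable men | Alpha | Power |
|---|---|---|
| 24 | 0.030 | 0.736 |
| 23 | 0.026 | 0.703 |
| 22 | 0.022 | 0.668 |
| 21 | 0.019 | 0.630 |
| 20 | 0.016 | 0.589 |

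Each lost pair costs between 3.3 and 4.1 points. Lowering the cutoff to 3 does not help: alpha would be 0.0755 even at 20 men.

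**Step 4: how unevaluable men are counted.** If they stay in the 24 as non-responders, at an assumed rate d lost independently of response, the response rate becomes 0.20 × (1 − d). For d = 10% this is 0.18, and P(X ≥ 4 | 24, 0.18) = 0.650. For d = 5%, 15% and 20%, power is 0.695, 0.601 and 0.550.

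With the cutoff fixed at 4, excluding these men gives the same power, because the count of responders is the same. What changes is the estimate: 4 responders with 22 usable pairs is 4/24 = 16.7% or 4/22 = 18.2%, with a different confidence interval.

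**The case against.** **The power gap is not a tissue problem.** A reader might infer that the fall from 0.818 comes from tissue loss. It does not: with all 24 men evaluable the exact power is already 0.736. Only the drop below 0.736 can be put down to lost pairs, and closing the tissue gap would not restore 0.818. This objection stands, and the two points are kept apart here.

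**No loss rate is given.** A reader might infer that 24 evaluable men will not be reached. The documents do not show that; loss could be nil. The target is not secured, which is a weaker statement.

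**There are safeguards.** It would be too strong to say that tissue goes unchecked. Criterion 10 opens by asking for evaluable tissue, Section 8.1.1.2 lists pre-treatment tissue among procedures to complete before dosing, and Appendix 3 expects paired specimens from every man. What remains is that formal sufficiency is not an eligibility condition and that the two sections do not agree.

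**Replacement is not absolutely barred.** If all four delayed-surgery replacements were used, 28 men could be analysed (alpha 0.049, power 0.840). But those places depend on surgical delay, so they are no provision for tissue failure.

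**Insufficient is not the same as unusable.** The 2-core, 15-slide standard serves all the correlative work, including PD-L1, Btk and receptor sequencing. Nothing says B-cell staining needs 15 slides, so a man below the standard may still have the powered endpoint. This also stands. Nor has every man agreed to a repeat biopsy: criterion 10 asks for that only when archival tissue is unavailable.

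**Conclusion.** The power statement in Section 12.3 is wrong as written: 24 evaluable men with a cutoff of 4 give alpha 0.030 and power 0.736, about 8 points below the claim. This rests only on the plan's own inputs and on reading the cutoff as four or more. It is tempting to explain 27 as the 24 men plus the 3 treated earlier at UCSF, but the documents do not say so, and the normal approximation is another possible origin.

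Separately, 24 evaluable men is not secured, because there is no enrolment allowance and no replacement for insufficient tissue, and Sections 3.3.1 and 8.1.1.2 conflict. The size is about 3 to 4 points per lost pair, starting from 0.736. The number lost is an assumption, and the 10% example (0.650) also assumes that loss is unrelated to response. The unspecified denominator affects the reported proportion and its interval. With the cutoff fixed at 4, it does not by itself change the power.

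**What to change.** 1. **Section 12.3:** replace 0.818 and 0.044 with the exact values at 24 evaluable men (power 0.736, alpha 0.030), state the cutoff as four or more, and give power for 20 to 24 evaluable men.
2. **Section 12.6:** state whether a dosed man without a usable biopsy/prostatectomy pair counts as a non-responder or is excluded, and use that denominator for the proportion and its 95% interval.
3. **Sections 3.3.1 and 8.1.1.2:** reconcile them so that archival tissue is confirmed usable for the B-cell endpoint within the 28-day screening window, before Day 1. The 15-slide standard should not become a trigger for new biopsies; it covers more than the powered endpoint and could impose an invasive procedure on men whose tissue is adequate for it.

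**Cost:** the stated power becomes less favourable, screening gains a slide check, and the protocol wording changes. These changes do not require a larger sample.
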